## PI-Sponsored FDA-Regulated Research

Is this an investigator-initiated study that:

**Back to Top** 

- 1) involves testing a Nonsignificant Risk (NSR) Device, or
- 2) is being conducted under an investigator-held Investigational New Drug (IND) or Investigational Device Exemption (IDE)?

○ Yes ○ No

#### PI-Sponsored FDA-Regulated Research

If the answer above is yes, then the investigator assumes the regulatory responsibilities of both the investigator and sponsor. The Office of Research Integrity provides a summary list of sponsor IND regulatory requirements for drug trials [PDF], IDE regulatory requirements for SR device trials [PDF], and abbreviated regulatory requirements for NSR device trials [PDF]. For detailed descriptions see FDA Responsibilities for Device Study Sponsors or FDA Responsibilities for IND Drug Study Sponsor-Investigators.

- Describe the experience/knowledge/training (if any) of the investigator serving as a sponsor (e.g., previously held an IND/IDE); and
- Indicate if any sponsor obligations have been transferred to a commercial sponsor, contract research organization (CRO), contract monitor, or other entity (provide details or attach FDA 1571).

IRB policy requires mandatory training for all investigators who are also FDA-regulated sponsors (see Sponsor-Investigator FAQs). A sponsor-investigator must complete the applicable Office of Research Integrity web based training, (drug or device) before final IRB approval is granted.

Has the sponsor-investigator completed the mandatory PI-sponsor training prior to this submission? • Yes • No

If the sponsor-investigator has completed equivalent sponsor-investigator training, submit documentation of the content for the IRB's consideration.

Attachments

HIPAA 0 unresolved comment(s)

Is HIPAA applicable? • Yes O No

(Visit ORI's Health Insurance Portability and Accountability Act (HIPAA) web page to determine if your research falls under the HIPAA Privacy Regulation.)

If yes, check below all that apply and attach the applicable document(s): 0

☐ HIPAA De-identification Certification Form ☐ HIPAA Waiver of Authorization

Attachments

#### STUDY DRUG INFORMATION

0 unresolved comment(s)

## The term drug may include:

- FDA approved drugs,
- unapproved use of approved drugs,
- · investigational drugs or biologics,
- other compounds or products intended to affect structure or function of the body, and/or
- complementary and alternative medicine products such as dietary supplements, substances generally recognized as safe (GRAS) when used to diagnose, cure mitigate, treat or prevent disease, or clinical studies of e-cigarettes examining a potential therapeutic purpose.

Does this protocol involve a drug including an FDA approved drug; unapproved use of an FDA approved drug; and/or an investigational drug?

If yes, complete the questions below. Additional study drug guidance.

Epidiolex	
(Oncology or Non-Oncology).	quired by Hospital Policy to utilize Investigational Drug Service (IDS) pharmacies Use of IDS is highly recommended, but optional for outpatient studies. Outpatient s are subject to periodic inspection by the IDS for compliance with drug accountabile.
Indicate where study drug(s)	will be housed and managed:
Investigational Drug Se	
Other Location:	
c Yes @ No	under a valid Investigational New Drug (IND) application?
If Yes, list IND #(s) and	complete the following:
IND Submitted/Held by:	
Sponsor: □	Held By:
·	Held By:
Sponsor: □	Held By:
Sponsor:  Investigator:  Other:  Checkmark if the sture IND) or if this is an Individual of the sture IND of the stude IND of the sture IND of the stude IND of	Held By:
Sponsor:  Investigator:  Other:  Checkmark if the studind in this is an Individual in the studing in the s	Held By:  Held By:  Held By:  Held By:  dy is being conducted under FDA's Expanded Access Program (e.g., Treatment vidual Patient Expanded Access IND (FDA Form 3926).

Complete and attach the required Study Drug Form picking "Study Drug Form" for the document type. Any applicable drug documentation (e.g., Investigator Brochure; approved labeling; publication; FDA correspondence, etc.) should be attached using "Other Drug Documentation" for the document type.

# Attachments

Attach Type	File Name
Study Drug	ori-f10900-form-o-investigational-drugs-
Form	pdf.pdf

#### STUDY DEVICE INFORMATION

0 unresolved comment(s)

#### A DEVICE may be a:

- · component, part, accessory;
- assay, reagent, or in-vitro diagnostic device;
- software, digital health, or mobile medical app;
- other instrument if intended to affect the structure or function of the body, diagnose, cure, mitigate, treat or prevent disease; or
- a homemade device developed by an investigator or other non-commercial entity and not approved for marketing by FDA.

For additional information, helpful resources, and definitions, see ORI's Use of Any Device Being Tested in Research web page.

Does this protocol involve testing (collecting safety or efficacy data) of a medical device including an FDA approved device, unapproved use of an approved device, humanitarian use device, and/or an investigational device?

∩ Yes ⊙ No

[Note: If a marketed device(s) is only being used to elicit or measure a physiologic response or clinical outcome, AND, NO data will be collected on or about the device itself, you may answer "no" above, save and exit this section, (Examples: a chemo drug study uses an MRI to measure tumor growth but does NOT assess how effective the MRI is at making the measurement; an exercise study uses a heart monitor to measure athletic performance but no safety or efficacy information will be collected about the device itself, nor will the data collected be used for comparative purposes against any other similar device).]

If you answered yes above, please complete the following questions.

Investigator: Held By:  Other: Held By:  Other: Held By:  Check if this is a Treatment IDE or Compassionate Use under the Food and Drug Administration (FDA) Expanded Access program.	and the state of Deputing Francisco the s	nder a valid Investigational Device Exemption (IDE),
If Yes, complete the following: IDE or HDE #(s)  IDE/HDE Submitted/Held by:  Sponsor:  Held By: Investigator:  Held By: Other:  Held By:	•	1 (HDE) or Compassionate use?
Sponsor: Held By:  Investigator: Held By:  Other: Held By:  Check if this is a Treatment IDE or Compassionate Use under the Food and Drug Administration	If Yes, complete the follow	ring:
Sponsor: Held By:  Investigator: Held By:  Other: Held By:  Check if this is a Treatment IDE or Compassionate Use under the Food and Drug Administration		
Sponsor: Held By:  Investigator: Held By:  Other: Held By:  Check if this is a Treatment IDE or Compassionate Use under the Food and Drug Administration		
Investigator: Held By: Held By: Check if this is a Treatment IDE or Compassionate Use under the Food and Drug Administration	IDE/HDE Submitted/Held I	by:
Other: Held By: Check if this is a Treatment IDE or Compassionate Use under the Food and Drug Administration	Sponsor: □	Held By:
■ Check if this is a Treatment IDE or Compassionate Use under the Food and Drug Administration	Investigator:	Held By:
	Other:	Held By:
For Individual or Small Group Expanded Access, see FDA's Early Expanded Access Program Information , and attach the following:	(FDA) Expanded Access For Individual or Small Gi	s program. roup Expanded Access, see FDA's Early Expanded Access Program

 
FDA expanded access approval or sponsor's authorization;
 
An independent assessment from an uninvolved physician, if available;
 
Confirmation of agreement from manufacturer or entity authorized to provide access to the product.
 
	
 
An independent asse
 
	essment from an uninvolved physician, if available;

Does the intended use of any research device being tested (not clinically observed) in this study meet the regulatory definition of Significant Risk (SR) device?

© Yes. Device(s) as used in this study presents a potential for serious risk to the health, safety, or welfare of a subject and (1) is intended as an implant; or (2) is used in supporting or sustaining human life; or (3) is of substantial importance in diagnosing, curing, mitigating or treating disease, or otherwise prevents impairment of human health; or (4) otherwise presents a potential for serious risk to the health, safety, or welfare of a subject.

No. All devices, as used in this study do not present a potential for serious risk to the health, safety, or welfare of subjects/participants.

Complete and attach the required Study Device Form, picking the "Study Device Form" for the document type. Any applicable device documentation (e.g., Manufacturer information; patient information packet; approved labeling; FDA correspondence, etc.) should be attached using "Other Device Documentation" for the document type.

Attachments

RESEARCH SITES 0 unresolved comment(s)

To complete this section, ensure the responses are accurate then click "SAVE".

A) Check all the applicable sites listed below at which the research will be conducted. If none apply, you do not need to check any boxes.

#### -UK Sites

- □ UK Classroom(s)/Lab(s)
- □ UK Clinics outside of Lexington
- □ UK Healthcare Good Samaritan Hospital

#### -Schools/Education Institutions

- □ Fayette Co. School Systems \*
- □ Other State/Regional School Systems
- ☐ Institutions of Higher Education (other than UK)

\*Fayette Co. School systems, as well as other non-UK sites, have additional requirements that must be addressed. See ORI's IRB Application Instructions - Off-site Research web page for details.

## Other Medical Facilities

- □ Bluegrass Regional Mental Health Retardation Board
- □ Cardinal Hill Hospital
- □ Eastern State Hospital
- □ Norton Healthcare
- □ Nursing Homes
- ☐ Shriner's Children's Hospital
- □ Veterans Affairs Medical Center
- ☐ Other Hospitals and Med. Centers
- □ Correctional Facilities
- ☐ Home Health Agencies
- □ International Sites

Research activities conducted at performance sites that are not owned or operated by the University of Kentucky, at sites that are geographically separate from UK, or at sites that do not fall under the UK IRB's authority, are subject to special procedures for coordination of research review. Additional information is required (see IRB Application Instructions - Off-Site Research web page), including:

- A letter of support and local context is required from non-UK sites. See *Letters of Support and Local Context* on the IRB Application Instructions Off-Site Research web page for more information.
- Supportive documentation, including letters of support, can be attached below.
- NOTE: If the non-UK sites or non-UK personnel are engaged in the research, there are additional federal and university requirements which need to be completed for their participation. For instance, the other site(s) may need to complete their own IRB review, or a cooperative review arrangement may need to be established with non-UK

56982

sites

 Questions about the participation of non-UK sites/personnel should be discussed with the ORI staff at [contact].

List all other	non-UK owned/operat	ed locations where th	e research will be	conducted:	
Describe the	role of any non-UK sit	te(s) or non-UK persor	nnel who will be pa	articipating in your r	esearch.
Attachments					
Is this a multi-site	study for which you a	re the lead investiga	ator or UK is the I	ead site? ∈Yes ⊚	No
•	ne plan for the manage interim results from the	, ,	anticipated probler	ns, noncompliance	, and submission of protocol

C) If your research involves collaboration with any sites and/or personnel outside the University of Kentucky, then it is considered multisite research and IRB reliance issues will need to be addressed. This may include national multi-center trials as well local studies involving sites/personnel external to UK. If you would like to request that the University of Kentucky IRB (UK IRB) serve as the lead IRB for your study, or if you would like the UK IRB to defer review to another IRB, please contact the [contact].

#### **RESEARCH ATTRIBUTES**

0 unresolved comment(s)

Indicate the items below that apply to your research. Depending on the items applicable to your research, you may be required to complete additional forms or meet additional requirements. Contact the ORI [contact]) if you have questions about additional requirements.

□ Not applicable

## -Check All That Apply

- □ Academic Degree/Required Research
- ☐ Alcohol/Drug/Substance Abuse Research
- □ Biological Specimen Bank Creation (for sharing)
- □ CCTS-Center for Clinical & Translational Science
- □ Certificate of Confidentiality
- □ Clinical Trial Phase 1
- $\hfill\Box$  Collection of Biological Specimens for internal banking and use (not sharing)
- □ Community-Based Participatory Research
- □ Deception
- □ Educational/Student Records (e.g., GPA, test scores)
- □ Emergency Use (Single Patient)
- ☐ Gene Transfer
- ☐ Genetic Research
- $\hfill\Box$  GWAS (Genome-Wide Association Study) or NIH Genomic Data Sharing (GDS)
- □ Human Cells, Tissues, and Cellular and Tissue Based Products
- ☐ Individual Expanded Access or Compassionate Use
- □ International Research
- □ Planned Emergency Research Involving Exception from Informed Consent
- □ Recombinant DNA
- □ Registry or data repository creation
- ☐ Stem Cell Research
- ☐ Suicide Ideation or Behavior Research
- □ Survey Research
- □ Transplants
- $\hfill\Box$  Use, storage and disposal of radioactive material and radiation producing devices
- □ Vaccine Trials

For additional requirements and information:

- Cancer Research (MCC PRMC)
- Certificate of Confidentiality (look up "Confidentiality/Privacy...")
- CCTS (Center for Clinical and Translational Science)
- Clinical Research (look up "What is the definition of....)
- Clinical Trial
- Collection of Biological Specimens for Banking (look up "Specimen/Tissue Collection...")
- Collection of Biological Specimens (look up "Specimen/Tissue Collection...")
- Community-Based Participatory Research (look up "Community-Engaged...")
- Data & Safety Monitoring Board (DSMB)

\*For Medical IRB: Service Request Form for CCTS DSMB

- Data & Safety Monitoring Plan
- Deception\*

\*For deception research, also go to the E-IRB Application Informed Consent section, checkmark and complete "Request for Waiver of Informed Consent Process"

- Emergency Use (Single Patient) [attach Emergency Use Checklist] (PDF)
- Genetic Research (look up "Specimen/Tissue Collection...")
- Gene Transfer
- HIV/AIDS Research (look up "Reportable Diseases/Conditions")
- Screening for Reportable Diseases [E2.0000] (PDF)
- International Research (look up "International & Non-English Speaking")
- NIH Genomic Data Sharing (GDS) Policy (PDF)
- Planned Emergency Research Involving Waiver of Informed Consent\*

\*For Planned Emergency Research Involving Waiver of Informed Consent, also go to the E-IRB Application Informed Consent section, checkmark and complete "Request for Waiver of Informed Consent Process"

• Use, storage and disposal of radioactive material and radiation producing devices

#### **FUNDING/SUPPORT**

0 unresolved comment(s)

If the research is being submitted to, supported by, or conducted in cooperation with an external or internal agency or funding program, indicate below all the categories that apply. ①

□ Not applicable

## Check All That Apply

- □ Grant application pending
- □(HHS) Dept. of Health & Human Services
  - (NIH) National Institutes of Health
- □ (CDC) Centers for Disease Control & Prevention
- □ (HRSA) Health Resources and Services
   Administration
- □(DoJ) Department of Justice or Bureau of Prisons
- □ (DoE) Department of Energy
- □ (EPA) Environmental Protection Agency
- □ Federal Agencies Other Than Those Listed Here
- ☐ Industry (Other than Pharmaceutical Companies)
- □ Internal Grant Program w/ proposal
- □ National Science Foundation
- □ Other Institutions of Higher Education
- □ Pharmaceutical Company
- ☐ Private Foundation/Association
- □ U.S. Department of Education
- □ State

Other:

Click applicable listing(s) for additional requirements and information:

- (HHS) Dept. of Health & Human Services
- (NIH) National Institutes of Health
- (CDC) Centers for Disease Control & Prevention
- (HRSA) Health Resources & Services Administration
- (SAMHSA) Substance Abuse & Mental Health Services Administration
- Industry (Other than Pharmaceutical Companies) [IRB Fee Info]
- National Science Foundation
- (DoEd) U.S. Department of Education
- (DoJ) Department of Justice or Bureau of Prisons
- (DoE) Department of Energy Summary and Department of Energy Identifiable Information Compliance Checklist
- (EPA) Environmental Protection Agency

Specify the funding source and/or cooperating organization(s) (e.g., National Cancer Institute, Ford Foundation, Eli Lilly & Company, South Western Oncology Group, Bureau of Prisons, etc.):

Markey Cancer Center

#### Add Related Grants

If applicable, please search for and select the OSPA Account number or Electronic Internal Approval Form (eIAF) # (notif #) associated with this IRB application using the "Add Related Grants" button.

If required by your funding agency, upload your grant using the "Grant/Contract Attachments" button.

Add Related Grants

**Grant/Contract Attachments** 

The research involves use of Department of Defense (DoD) funding, military personnel, DoD facilities, or other DoD resources. (See DoD SOP and DoD Summary for details)

○ Yes ○ No

Using the "attachments" button (below), attach applicable materials addressing the specific processes described in the DoD SOP.

DOD SOP Attachments

Additional Certification: (If your project is federally funded, your funding agency may request an Assurance/ Certification/Declaration of Exemption form.) Check the following if needed:

□ Protection of Human Subjects Assurance/Certification/Declaration of Exemption (Formerly Optional Form – 310)

Assurance/Certification Attachments

#### **OTHER REVIEW COMMITTEES**

0 unresolved comment(s)

If you check any of the below committees, additional materials may be required with your application submission.

Does your research fall under the purview of any of the other review committees listed below? [If yes, check all that apply and attach applicable materials using the attachment button at the bottom of your screen.]

c Yes ∈ No

- □ Institutional Biosafety Committee
- □ Radiation Safety Committee
- □ Radioactive Drug Research Committee
- ☐ Graduate Medical Education Committee (GME)
- ☐ Office of Medical Education (OME)

#### **Additional Information**

- Institutional Biosafety Committee (IBC) Attach required IBC materials
- Radiation Safety Committee (RSC) For applicability, see instructions and attach form
- Radioactive Drug Research Committee (RDRC)
- Markey Cancer Center (MCC) Protocol Review and Monitoring Committee (PRMC)\*\* - Attach MCC PRMC materials, if any, per instructions.
- Office of Medical Education (OME)
- Graduate Medical Education Committee (GME)

#### Attachments

\*\* If your study involves cancer research, be sure to select "Cancer Research" in the "Research Attributes" section. ORI will send your research protocol to the Markey Cancer Center (MCC) Protocol Review and Monitoring Committee (PRMC). The MCC PRMC is responsible for determining whether the study meets the National Cancer Institute (NCI) definition of a clinical trial and for issuing documentation to you (the investigator) which confirms either that PRMC approval has been obtained or that PRMC review is not required. Your IRB application will be processed and reviewed independently from the PRMC review.

# 9. STATISTICAL CONSIDERATIONS

# 9.1 Study Design/Endpoints

This is a phase I dose escalation study with expansion cohort. Dose escalation will be determined by a Bayesian optimal interval (BOIN) design [41]. The target DLT rate is 30%. Patients are enrolled in cohorts with 3 patients in each cohort. Enrollment will be temporarily halted after the last patient of each cohort is enrolled until all current patients are DLT evaluable or withdrawn from the study. A patient will be considered DLT evaluable if he completes at least 75% of the planned dose of Epidiolex in the first 30 days of the treatment, unless the reason is due to toxicity.

The primary objective is to evaluate the acute toxicity and long-term safety and tolerability of Epidiolex (CBD) in patients with biochemically recurrent prostate cancer. Acute toxicity of Epidiolex is evaluated through DLT rate, which is calculated as the total number of patients experienced DLTs at a dose level divided by the total number of patients treated at the corresponding dose level. The calculation of DLT rate will only include DLT evaluable patients. Patients who are not DLT-evaluable will not be replaced for the current cohort and will not be included in the calculation of DLT rate. At the end of the dose escalation part of the study, we will use the dose escalation/de-escalation decision rules (see section 9.1.1) to decide the dose level for dose expansion cohort. If the current dose at the end of dose escalation is already the highest available dose, and the decision rules did not indicate de-escalation or elimination, the highest dose level is deemed as safe for acute toxicity; otherwise, the dose recommended by the decision rule is the estimated MTD.

Following dose-escalation, an expansion cohort will be enrolled to confirm safety for acute toxicity, evaluate long-term safety and tolerability and explore evidence of efficacy of the study treatment. Long-term safety and tolerability are evaluated through the summary statistics of adverse events occurred within the 90-day follow-up period in patients who received any amount of study drug. The study treatment is deemed as not safe for long-term tolerability if any of the following criteria are met:

- More than 40% of the patients treated at the dose level selected for expansion cohort experienced grade 3 or higher AEs that are possibly/probably/definitely related to study treatment
- More than 30 % of the patients experienced grade 3 or higher CNS toxicity that are possibly/probably/definitely related to study treatment

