#### 9.1.1 Dose Escalation / De-escalation Decision Rule

	Number of patients Treated									
Decision Rule	1	2	3	4	5	6	7	8	9	
Escalate (or highest) if # DLT <=	0	0	0	0	1	1	1	1	2	
De-escalate (or lowest) if # DLT >=	1	1	2	2	2	3	3	3	4	
Eliminate (or stop) if # DLT >=			3	3	4	4	5	5	5	

Note: the next cohort will be treated at the current dose level if the criteria are not met for escalation/de-escalation rules.

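### SAP 9.1 decides DLT evaluability by why doses were missed, not by whether a DLT occurred, so a DLT in a man short of 75% for a non-toxicity reason is discarded and 1/3 (stay) is scored as 0/2 (escalate)

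*Combined protocol and SAP*

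**What the plan says.** For a man to be evaluable for DLT, SAP 9.1 requires "at least 75% of the planned dose of Epidiolex in the first 30 days of the treatment, unless the reason is due to toxicity". So the exception turns on the cause of the shortfall.

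Two further sentences in 9.1 fix the consequence: "The calculation of DLT rate will only include DLT evaluable patients", and "Patients who are not DLT-evaluable will not be replaced for the current cohort and will not be included in the calculation of DLT rate". Cohorts are of three and the target DLT rate is 30%.

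SAP 9.1.1 gives the decision table for 1 to 9 treated patients, with the rows "Escalate (or highest) if # DLT <=", "De-escalate (or lowest) if # DLT >=" and "Eliminate (or stop) if # DLT >="; if neither the escalation nor the de-escalation limit is met, the next cohort stays at the current dose. SAP 9.3 rests both the dose decisions and the MTD on this table.

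The IRB application (Research Description, Study Design) has a different rule: completion of 75% of doses, no exception for toxicity, and replacement of men who are not evaluable.

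**The concern.** A dose-escalation rule normally lets two kinds of patient inform the decision: those who had a DLT, at whatever exposure, and those who had enough exposure without one. SAP 9.1 states the second condition and adds an exception for shortfalls caused by toxicity, but leaves out the first. A man who misses doses through travel, poor adherence or a personal decision, and who also has a DLT in the 30 days, has a shortfall that toxicity did not cause. He is then not evaluable, and his DLT leaves the numerator and the denominator.

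A DLT on reduced exposure is no weaker as evidence of toxicity than one on full exposure. The DLT rate is the only input to the table, escalation uses about nine evaluable men, and cohorts have three, so one discarded event can change the dose given to the next cohort.

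**Working it through.** **1. Reproduce the table.** Inputs: target φ = 0.30 (SAP 9.1), with the usual BOIN settings φ1 = 0.6φ = 0.18 and φ2 = 1.4φ = 0.42. These two settings are assumed; the documents do not state them.

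- Escalation limit: ln(0.82/0.70) / ln[(0.30×0.82)/(0.18×0.70)] = 0.2365
- De-escalation limit: ln(0.70/0.58) / ln[(0.42×0.70)/(0.30×0.58)] = 0.3585
- Elimination: Pr(p > 0.30) > 0.95 under a Beta(1,1) prior, from n = 3

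Escalating at floor(0.2365n), de-escalating at ceil(0.3585n) and applying the elimination rule reproduces every cell of the 9.1.1 table. The table itself is sound; the issue is what is fed into it.

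**2. Effect of discarding one DLT.** The score k/n becomes (k−1)/(n−1). Examples read from the table:

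| All DLTs counted | DLT discarded |
|---|---|
| 1/3: stay | 0/2: escalate |
| 1/4: stay | 0/3: escalate |
| 2/6: stay | 1/5: escalate |
| 3/3: eliminate | 2/2: de-escalate |

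For n = 2 to 9 and k = 1 to n there are 2+3+…+9 = 44 cells. In 15 the decision becomes less cautious, in 29 it is unchanged, and in none does it become more cautious. The table has columns for n = 1 and n = 2 and men are not replaced within the cohort, so a 0/2 decision can be used under the plan.

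**3. Illustrative size in a first cohort of three.** Let q be the share of men short of 75% for a non-toxicity reason, independent of DLT. The documents give no figure; q = 10% to 30% is assumed. With true DLT rate p:

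- SAP rule: P(escalate) = [q + (1−q)(1−p)]³ − q³
- Every DLT kept: P(escalate) = (1−p)³ − [(1−p)q]³

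For p = 0.30 and q = 0.20: 0.76³ − 0.20³ = 0.431, against 0.70³ − 0.14³ = 0.340.

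| True DLT rate | q = 10%: SAP / DLTs kept | q = 20% | q = 30% |
|---|---|---|---|
| 0.30 | 0.388 / 0.343 | 0.431 / 0.340 | 0.466 / 0.334 |
| 0.45 | 0.210 / 0.166 | 0.254 / 0.165 | 0.294 / 0.162 |
| 0.60 | 0.096 / 0.064 | 0.133 / 0.064 | 0.168 / 0.062 |

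**4. The other side of the ledger.** With every DLT kept and short-exposure DLT-free men still dropped, the expected scored rate is p / [p + (1−p)(1−q)]. For p = 0.30 this is 0.30/0.93 = 0.323 at q = 10% and 0.30/0.86 = 0.349 at q = 20%.

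First-cohort probability of de-escalation, elimination included, at p = 0.30 and q = 20%:

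- SAP rule: 0.512×0.216 + 0.384×0.51 + 0.096×0.30 = 0.335
- DLTs kept: (0.027 + 3×0.09×0.56) + 3×0.14×(0.09 + 2×0.30×0.56) + 3×0.14²×0.30 = 0.375

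**The case against.** **The case is rare.** A man whose drug is held or stopped because of his DLT has a shortfall due to toxicity and remains evaluable. The event is lost only when the shortfall has another cause, or mixed causes that the wording does not settle. This stands, and it limits how often the problem arises. It does not change what the rule does when it arises.

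**Another section may cover it.** The DLT definition is not in the supplied text and could say that any man with a DLT is evaluable. That is possible, but SAP 9.1 as written does not say so or point to such a sentence.

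**There are backstops.** The 90-day criteria in 9.1 cover all men who took any drug, the monitoring committee reviews serious adverse events and dose levels, and 9.2 adds cohorts if three or more of the first nine men are not evaluable. A discarded DLT would not be invisible. None of these sets the decision for the next cohort.

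**A reader might infer a systematic downward bias in the DLT rate.** The documents do not support that. The same rule also drops DLT-free men with a non-toxicity shortfall. If such shortfalls are independent of DLT, the expected rate among evaluable men stays at the true value. The higher chance of escalation then comes from deciding on fewer men, and de-escalation also becomes more likely: at p = 0.30, from 0.189 + 0.027 = 0.216 with everyone counted to 0.335 at q = 20%.

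**A reader might also infer that the toxicity exception is itself wrong,** since a man who stops for toxicity below the DLT threshold is scored as DLT-free. That depends on the DLT definition, which may already count such dosing failure. Excluding him would turn 0/3 into 0/2, which is still escalate, and would leave no decision if all three men stopped. SAP 9.1 keeps these men by an explicit choice, and the trade-off can be argued either way.

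**Conclusion.** The gap is real and narrow. On the wording of SAP 9.1, a DLT in a man short of 75% for a non-toxicity reason is discarded, and the table can then call for escalation where the full data call for staying. The direction for a discarded DLT follows from the table alone: 15 of 44 cells less cautious, none more cautious.

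The size rests on an assumed q and on independence from DLT. At a true rate of 0.30, the first-cohort chance of escalating is 0.388 to 0.466 under the SAP rule, against 0.343 to 0.334 with every DLT kept, for q from 10% to 30%. The finding does not extend to a general bias in the DLT rate or to men who stop for toxicity below DLT. It would fall away if the DLT section, not available here, already makes every man with a DLT evaluable.

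**What to change.** In SAP 9.1, state that a patient is DLT evaluable if he has a DLT at any time in the first 30 days, whatever dose he received, or if he meets the existing 75% rule with its toxicity exception. Reconcile the evaluability and replacement wording in the IRB application (Study Design) with this. Read literally, that text would remove even a man stopped by a DLT before 75%.

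For men who stop for toxicity below DLT, keep the current handling unless the DLT definition says otherwise; at most, report their number with each cohort decision.

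The drafting cost is a sentence in each document. The statistical cost should be stated openly: keeping every DLT while still dropping short-exposure DLT-free men raises the scored rate above the true one (for 0.30, about 0.32 at q = 10% and 0.35 at q = 20%) and makes first-cohort de-escalation somewhat more likely (0.335 to 0.375 at q = 20%). That is a cautious error, and the sponsor should accept it knowingly.
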